### **4.5 Withdrawal and Replacement of Subjects**

#### **4.5.1 Premature Subject Withdrawal**

The subjects' legal guardians have the right to withdraw the subject from the study at any time for any reason, without the need to justify their decision. The investigator also has the right to withdraw subjects in case of AEs, protocol violations, or other reasons. Since an excessive rate of withdrawal can render the study non-interpretable, the unnecessary withdrawal of subjects must be avoided.

For any discontinuation after study entry, the investigator will obtain all the required details and document the reason(s) for discontinuation in the CRF. If the reason for withdrawal of a subject is an AE, the main specific event or laboratory test will be recorded in the CRF, and the investigator will make thorough efforts to clearly document the outcome.

If possible, the Study Completion Visit should be performed.

#### **4.5.2 Subject Replacement Policy**

The study will recruit patients until a minimum of 12 subjects have undergone PK assessment, 6 subjects (at least 3 subjects aged between 0 and <6 years and 3 subjects aged between 6 and <12 years) have at least one documented bleeding episode, and a minimum of 2 surgical procedures have been documented. Patients with no documented bleeding episode, e.g., those only receiving PK treatment or those withdrawn for safety reasons before the first bleeding, will be replaced.

### **4.6 Assignment of Subjects to Treatment Groups**

Not applicable.

#### **4.7 Relevant Protocol Deviations**

In the case of any major protocol deviation or violation, the investigator and Octapharma will decide on the further participation of the subject in this study, after having discussed all relevant aspects.

#### **4.8 Subsequent Therapy**

In case the bleeding is not effectively stopped or surgical prophylaxis is deemed not to be adequate after the recommended *Octafibrin* dosing as judged by the investigator (see Section 5.4), the subject may receive a different licensed fibrinogen concentrate (e.g., Haemocomplettan P®/RiaSTAP™) or whatever the investigator considers standard of care.

## 5 INVESTIGATIONAL MEDICINAL PRODUCT

### 5.1 Characterisation of Investigational Product

*Octafibrin* is a human plasma-derived fibrinogen concentrate for intravenous use. Its ingredients are listed in Table 1.

**Table 1: Composition of *Octafibrin***

Ingredients	Quantity per mL reconstituted solution, mean values	Standard
Active ingredient		
Fibrinogen as clottable protein	20 mg	Ph. Eur.
Excipients		
Sodium chloride	6 mg	Ph. Eur.
Sodium citrate dehydrate	1.5 mg	Ph. Eur.
Glycine	10 mg	Ph. Eur.
L-arginine hydrochloride	10 mg	Ph. Eur.

Ph. Eur. = Pharmacopoeia Europaea.

*Octafibrin* is a powder for solution for injection supplied in labelled 100 mL vials to be reconstituted with 50 mL sterile Water for Injection (WFI).

Several batches of the product will be used in the study. The batch numbers will be reported in the final study report.

The final product will be released by the responsible Octapharma Quality Control Department, according to a defined final product specification.

### 5.2 Packaging and Labelling

The open-label study design does not necessitate the blinding of study participants or study site personnel to treatment information.

The IMP will be labelled according to GMP Annex 13. Final labelling and packaging will comply with the national requirements of each country where the study is to be conducted.

### 5.3 Conditions for Storage and Use

The IMP has to be stored at 2°C to 8°C and protected from light. The product must not be frozen. The investigator/authorised personnel at the site will ensure that the IMP is stored in appropriate conditions with restricted access and in compliance with national regulations.

### 5.4 Dose and Dosing Schedule

In this study, *Octafibrin* will be administered as **intravenous (i.v.) bolus injection**. Continuous infusion is not allowed.

#### 5.4.1 PK Dose Schedule and Mode of Administration

For PK assessments, subjects will receive a single intravenous infusion of 70 mg/kg body weight of *Octafibrin*.

#### 5.4.2 Octafibrin Treatment Dose Calculation

*Octafibrin* will be individually dosed to achieve a recommended target fibrinogen plasma level dependent on the type of bleeding or surgery (minor or major). The dose will be calculated individually as follows:

$$\text{Fibrinogen dose (mg/kg body weight)} = \frac{[\text{Target peak plasma level (mg/dL)} - \text{measured level (mg/dL)}**]}{\text{Median response* (mg/dL per mg/kg body weight)}}$$

\*The median response in this dose calculation formula is the median incremental in vivo recovery reported for the PK of Octafibrin in the final analysis of study FORMA-01 which was calculated as 1.77 (g/L / mg/kg).

\*\*The measured level for the first infusion will be the historical level for that patient after a washout or, if below the limit of detection of the local assay, zero (0) will be used.

#### 5.4.3 Dosing for On-demand Treatment of Bleeding

For each bleeding episode that is treated as part of the study, each subject will receive at least 1 infusion of *Octafibrin* for the treatment of a major or minor acute bleeding episode on Day 1.

*Octafibrin* will be individually dosed to achieve a recommended target fibrinogen plasma level dependent on the bleeding type (minor or major).

- **Minor bleeding** will be treated to achieve a recommended target fibrinogen plasma level of 100 mg/dL and an accepted lower limit of 80 mg/dL.
- **Major bleeding** will be treated to achieve a recommended target fibrinogen plasma level of 150 mg/dL and an accepted lower limit of 130 mg/dL.

On subsequent study days, fibrinogen plasma levels will be measured daily to determine whether additional infusions of *Octafibrin* are needed:

- **Minor bleeding** will be observed for at least 3 days.
- **Major bleeding** will be observed for at least 7 days.

#### Additional Octafibrin infusions, as required

- Additional infusions of *Octafibrin* **should** be administered if the actual fibrinogen plasma level measured on subsequent study days is below the accepted lower limit of the target level (80 mg/dL for minor bleeding, 130 mg/dL for major bleeding).
- If the actual fibrinogen plasma level is above the accepted lower limit of the target level, *Octafibrin* **should not** be administered.

### Definition of minor and major bleeding

- **Minor bleeding** events are defined as mild haemarthrosis or superficial muscle, soft tissue, and oral bleeding.
- **Major bleeding** events are defined as symptomatic bleeding in a critical area or organ, such as intracranial, intraspinal, intraocular, retroperitoneal, intraarticular, or pericardial bleeding, or intramuscular bleeding with compartment syndrome, or bleeding causing a decrease in haemoglobin level by 20 g/L (1.24 mmol/L) or more.

Characterisation of any other bleeding events not within these categories will be discussed individually with the investigator.

#### 5.4.4 Dosing for Surgery

For each surgery that is treated as part of the study, within 3 hours prior to surgery, subjects will receive a loading infusion of *Octafibrin*.

*Octafibrin* will be individually dosed to achieve a recommended target fibrinogen plasma level dependent on the surgery type (minor or major).

- Patients undergoing **minor surgery** will be treated to achieve a recommended target fibrinogen plasma level of 100 mg/dL and an accepted lower limit of 80 mg/dL.
- Patients undergoing **major surgery** will be treated to achieve a recommended target fibrinogen plasma level of 150 mg/dL and an accepted lower limit of 130 mg/dL.

On each post-operative day, fibrinogen plasma levels will be measured daily to determine whether maintenance infusions of *Octafibrin* are needed.

- **Minor surgery** will be observed for at least 3 post-operative days.
- **Major surgery** will be observed for at least 7 post-operative days.

#### Maintenance infusions, as required:

- Additional infusions of *Octafibrin* **should** be administered if the actual fibrinogen plasma level measured on subsequent study days is below the accepted lower limit of the target level (80 mg/dL for minor surgery, 130 mg/dL for major bleeding).
- If the actual fibrinogen plasma level is above the accepted lower limit of the target level, *Octafibrin* **should not** be administered.

#### Definition of minor and major surgery

Surgeries are defined as **major**, if any of the following criteria are met:

- Requiring general or spinal anaesthesia
- Requiring opening into the great body cavities
- In the course of which hazards of severe haemorrhage is possible
- Requiring haemostatic therapy for at least 6 days
- Orthopaedic interventions involving joints (ankle, knee, hip, wrist, elbow, shoulder)
- Surgeries/conditions in which the subject's life is at stake

Characterisation of any other surgery not within these categories and considered major by the investigator will be discussed individually with the investigator.

All other surgeries are classified as **minor**.

The classification is made prospectively.

## 5.5 Preparation and Method of Administration

### 5.5.1 Preparation

Each vial of *Octafibrin* will be reconstituted with 50 mL WFI. The solvent (i.e., WFI) and the concentrate in the closed vials must be warmed up to room temperature. Room temperature must be maintained during reconstitution. *Octafibrin* dissolves at room temperature to an almost colourless and slightly opalescent solution within 30 minutes. If the solution is cloudy or contains particulates, it should not be used. The solution should not be frozen.

*Octafibrin* should be administered immediately after reconstitution at a rate not exceeding 5 mL per minute. *Octafibrin* should not be mixed with other medicinal products or intravenous solutions.

### 5.5.2 Method of Administration

*Octafibrin* will be administered as intravenous (i.v.) bolus injection not exceeding an injection rate of 5 mL per minute.

**NOTE:** In this study, **only bolus injections** of *Octafibrin* are permitted. Continuous infusion is not allowed.

## 5.6 Blinding, Emergency Envelopes, and Breaking the Study Blind

Not applicable.

## 5.7 Drug Dispensing and Accountability

A drug dispensing log and the inventory will be kept current by the investigator, detailing the dates and quantities of IMP received at the site/pharmacy, and dispensed to each subject. The inventory will be available to the monitor to verify drug accountability during the study. Any unused or partially used IMP, including empty containers (if possible), will be accounted for.

Unused IMP may be destroyed at the study site, however, only after drug accountability has been verified and fully re-conciliated and written approval from the Sponsor has been obtained. Unused IMP can be returned to the Sponsor for destruction when drug accountability has been verified and fully re-conciliated and written approval from the Sponsor has been received.

## 5.8 Assessment of Treatment Compliance

Treatment compliance will be measured in terms of the subject receiving an infusion of *Octafibrin* from the study personnel. Administered doses of *Octafibrin* will be recorded for every infusion, including dates, times, and batch numbers; the batch numbers will be reported in the final study report.

## 6 STUDY CONDUCT

### 6.1 Observations Performed Throughout the Study

Patients identified by the study sites as potential study participants will be screened for inclusion into the study. The screening assessments will be performed as summarised in Section 6.1.1.

The PK assessments are summarised in Section 6.1.2. The assessments for patients enrolled and then having on-demand treatment of an active bleeding episode are summarised in Section 6.1.3. The assessments for patients planning to undergo elective surgery are summarised see Section 6.1.4.

All treated patients will undergo a Study Completion Visit as summarised in Section 6.1.5.

#### 6.1.1 Screening Assessments

Patients identified by the study sites as potential study participants will undergo the following screening assessments:

- Inclusion and exclusion criteria, including written informed consent for participation in the study by the subject's legal guardian
- Demography, medical history (including details concerning allergic tendencies), review of previous therapy

**NOTE:** If the period between screening and first treatment of acute bleeding or surgical prophylaxis is more than 3 months, informed consent will be re-reviewed and confirmed prior to treatment, and details of the review process will be recorded in the patient chart and indicated in the CRF by the investigator. Also, inclusion/exclusion criteria will be confirmed prior to treatment.

#### 6.1.2 Assessments During the PK Phase

Within 2 weeks after the screening process, subjects will receive a single infusion of 70 mg/kg *Octafibrin* on Day 1 of PK testing (PK-Day 1). Before the start of the PK phase, there must be an at least 2-week wash-out period of any fibrinogen containing product.

Before first injection vital signs and blood draws for baseline fibrinogen levels will be assessed. Retention serum samples for potential retesting will be collected within 30 minutes before infusion. At 1 and 3 hours post-infusion, vital signs and fibrinogen for PK will be assessed, and AEs will be recorded. Subjects will be further followed on:

#### **PK-Days 2 (24 hrs), 4 (72 hrs), 7 (144 hrs), and 10 (216 hrs)**

- Fibrinogen for PK
- Recording of AEs, including potential thromboembolic events

## PK-Day 14 (312 hrs)

- Fibrinogen for PK
- Vital signs
- Physical examination, including any signs or symptoms of potential thromboembolic events
- Recording of AEs, including potential thromboembolic events

The flow chart of assessments for the PK phase is provided on page xxiv.

**NOTE:** All adverse events (AEs, see Section 7.4), including thromboembolic events and early signs of allergic or hypersensitivity reactions, occurring between the start of the first *Octafibrin* infusion and the end of the PK phase will be recorded.

All SAEs occurring after the first IMP infusion will be documented and reported for a patient throughout the duration of the patient's participation in the study or as required to meet local regulations.

### 6.1.3 Assessments in Subjects Undergoing On-demand Treatment of Bleeding

Subjects presenting to the study site for an acute bleeding episode will undergo a 30-day observation and follow-up period as outlined below. Throughout the study, subjects may undergo more than one 30-day observation and follow-up periods for treatment of additional bleeding episodes as required until the close of the study. At the end of their study participation, patients will be asked to return for a final Study Completion Visit.

For information on the dose calculation and a definition of minor and major bleeding, see Section 5.4.3. The flow chart of assessments for on-demand treatment is provided on page xxii.

**NOTE:** All adverse events (AEs, see Section 7.4), including thromboembolic events and early signs of allergic or hypersensitivity reactions, occurring between the start of the first *Octafibrin* infusion and the end of each 30-day observation and follow-up period will be recorded. The detection of thromboembolic events will be supported by completing a TEE questionnaire at each study visit for the treatment of bleeding episodes and for surgeries. Concomitant medications will also be recorded throughout each 30-day observation and follow-up period. Administered doses of *Octafibrin* will be recorded for every infusion, including dates, times, and batch numbers.

All SAEs occurring after the first IMP infusion will be documented and reported for a patient throughout the duration of the patient's participation in the study or as required to meet local regulations. Also, any concomitant medications used to treat an SAE will be recorded.

#### 6.1.3.1 Day 1 (first day of treatment)

For subjects requiring on-demand treatment, Day 1 is the day they present for treatment of an acute bleeding episode.

### Pre-infusion assessments

The following assessments will be performed before the first infusion of *Octafibrin* for each bleeding episode:

- Medical history (including details of any non-study bleeding episodes and therapy), and prior/concomitant medication
- Characterisation of bleeding episode
- Vital signs
- Physical examination
- TEE questionnaire
- Height and weight
- Blood draw for:
  - fibrinogen plasma level (local lab–activity; central lab–antigen and activity; within 30 minutes before infusion)
  - MCF (within 30 minutes before infusion)
  - safety lab (local–haematology and clinical chemistry)
  - thrombogenicity
  - immunogenicity

**NOTE:** If the period between screening and first treatment of acute bleeding is more than 3 months, informed consent will be re-reviewed and confirmed prior to treatment, and details of the review process will be recorded in the patient chart and indicated in the CRF by the investigator. Also, inclusion/exclusion criteria will be confirmed prior to treatment.

### First infusion of Octafibrin

After the pre-infusion assessments, subjects will receive the first infusion of *Octafibrin* for treatment of bleeding (see Section 5.4).

### Post-infusion assessments

On Day 1, the following post-infusion assessments will be performed:

#### 1 hour ( $\pm 15$ minutes) after the end of infusion:

- Vital signs
- TEE questionnaire
- Blood draw for:
  - fibrinogen plasma level (local lab–activity; central lab–antigen and activity)
  - MCF
- AEs and concomitant medications

3 hours ( $\pm 15$  minutes) after the end of infusion:

- Vital signs
- TEE questionnaire
- Blood draw for:
  - fibrinogen plasma level (central lab—antigen and activity)
  - thrombogenicity
- AEs and concomitant medications

**NOTE:** If, in the investigator's judgement, the infusion of *Octafibrin* administered on Day 1 is deemed the only infusion needed for treatment of the subject's bleeding event, the subject will need to reach the end of the treatment observation period, where the "24 hours (i.e., 1 day) after the last infusion" assessments should be performed.

**6.1.3.2 All Study Days after Day 1 (Treatment Observation Period)**

Each subject's **treatment observation period** is defined according to the severity of the event and will last at least **3 days for minor and 7 days for major bleeding episodes**. If the patient requires multiple infusions, the actual treatment duration will be determined by the investigator based on his/her judgement of the subject's condition, and the treatment observation period will last until 24 hours after the last infusion.

**Daily assessments (for at least 3 days for minor bleeding or 7 days for major bleeding)**

- TEE questionnaire
- Blood draw for:
  - fibrinogen plasma level (local lab—activity; central lab—antigen and activity): Based on local lab results, the investigator will determine whether additional infusions of *Octafibrin* are needed.
  - safety lab (local—haematology)
- AEs and concomitant medications

**Octafibrin infusion, as required**

After these daily assessments, additional IMP dosing should occur as required depending on the actual and target plasma levels based on the following criteria:

- If the actual fibrinogen plasma level is below the accepted lower limit of the target fibrinogen plasma level (80 mg/dL for minor bleeding, 130 mg/dL for major bleeding; see Section 5.4), the subject should receive another infusion of *Octafibrin*.
- If the fibrinogen plasma level is greater than or equal to the accepted lower limit of the target fibrinogen plasma level, *Octafibrin* **should not** be administered on that day.

### **Pre- and post-infusion assessments**

If the subject receives an additional infusion of *Octafibrin*, the following pre- and post-infusion assessments will be performed:

#### *Pre-infusion assessments:*

- TEE questionnaire
- Blood draw for (within 30 minutes before infusion):
  - fibrinogen plasma level (local lab–activity; central lab–antigen and activity)
  - thrombogenicity

#### *1 hour ( $\pm$ 15 minutes) after the end of each infusion:*

- Vital signs
- TEE questionnaire
- Blood draw for:
  - fibrinogen plasma level (local lab–activity; central lab–antigen and activity)
  - thrombogenicity

**NOTE:** If, in the investigator's judgement, there are no additional infusions of *Octafibrin* needed to treat the bleeding event, the subject will need to reach the end of the treatment observation period, where the "24 hours (i.e., 1 day) after the last infusion" assessments should be performed.

#### **6.1.3.3 Last Infusion or End of the Observation Period (whichever comes last)**

If a patient requires multiple infusions for a bleeding event as defined by the investigator based on his/her judgement of the subject's condition, or the subject comes to the end of the observation period (whichever comes last), the following assessments will be performed:

### **Pre-infusion assessments**

The following assessments will be performed prior to the last infusion of *Octafibrin* if multiple infusions are needed:

- TEE questionnaire
- Blood draw for (within 30 minutes before infusion):
  - fibrinogen plasma level (local lab–activity; central lab–antigen and activity)

### **Last infusion of Octafibrin**

Following the pre-infusion assessments, subjects will receive their last infusion of *Octafibrin* depending on the actual and target plasma levels (see Section 5.4).

### Post-infusion assessments

On the Day of Last Infusion, post-infusion assessments will be as follows:

1 hour ( $\pm 15$  minutes) after the end of last infusion:

- Vital signs
- TEE questionnaire
- Blood draw for:
  - fibrinogen plasma level (local lab–activity; central lab–antigen and activity)

24 hours (i.e., 1 day) after the last infusion or at the end of the treatment observation period (whichever comes last)

- Vital signs
- Physical examination
- TEE questionnaire
- Blood draw for:
  - fibrinogen plasma levels (central lab–antigen and activity)
- Final assessment of haemostatic efficacy by the investigator with respect to the adequacy of stopping an acute bleed. The assessment is to include the entire period from the start of the first infusion until 24 hours (i.e., 1 day) after the last infusion and includes the clinical condition of the subject, laboratory values such as haematocrit and haemoglobin, and any additional haemostatic treatments (see Section 7.2.1).
- AEs and concomitant medications

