### **3.1.2.3 Safety Endpoints**

The following safety parameters will be calculated as secondary safety endpoints:

- Vital signs
- Physical examination
- Thromboembolic event (TEE) questionnaire
- Routine clinical laboratory assessment, including coagulation parameters
- Adverse events (AEs), including thromboembolic complications and early signs of allergic or hypersensitivity reactions
- Thrombogenicity testing before and after each IMP infusion for the treatment of bleeding, except on the Day of Last Infusion
- Immunogenicity testing before the first infusion of IMP and on Day 30 after the treatment of each bleeding episode

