**Table 5: Test Parameters and Laboratories**

Test	Material needed	Responsible laboratory
Fibrinogen activity (Clauss)	Citrated plasma	Local and central
Fibrinogen:Ag	Citrated plasma	Central
Fibrinogen inhibitor testing	Citrated plasma	Central
Clinical chemistry	Serum	Local
Haematology	EDTA blood	Local
Maximum clot strength	Citrated plasma	Central
Thrombogenicity (D-dimer, prothrombin fragment 1+2) 	Citrated plasma	Central

 Any thromboembolic events reported from Day 1 to Day 30 will be documented as AEs. A final clinical evaluation of any signs or symptoms of potential thromboembolic events will be done at Day 30.

All remaining serum and plasma volumes will be labelled and stored as retention samples at the central laboratory for at least 24 months after the completion of the study and until Octapharma's written authorisation to destroy these samples. These samples may be used for additional coagulation and viral testing, if needed.

The flow chart of assessments for on-demand treatment is provided on page xxii. The flow chart of assessments for surgical prophylaxis is provided on page xxiii.

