## 12 EVALUATION OF SAFETY PARAMETERS

The analysis of safety will be based on the safety population.

All AEs (including events likely to be related to the underlying disease, or a concomitant illness or medication or clinically significant abnormalities in laboratory parameters or vital signs) will be displayed in summary tables and listings.

Incidences of adverse events will be given as numbers and percentages of subjects with:

- Any AE.
- Any SAE.
- Any AE probably or possibly related to the IMP.
- Any AE temporally related (within 24 hours after end of infusion) to the IMP.
- Any severe AE.
- Any withdrawal due to AE.
- Any AE by Medical Dictionary for Regulatory Activities (MedDRA) preferred term (descending frequency).
- Any AE temporally related (within 24 hours after end of infusion) by MedDRA preferred term (descending frequency).
- Any AE by MedDRA system organ class (SOC).
- Any AE temporally related (within 24 hours after end of infusion) by MedDRA SOC.

Summary tables for AEs will be given by SOC and preferred term. Additionally, AEs will be summarised by severity and relationship to the IMP.

The MedDRA coded terms and the corresponding original (verbatim) terms used by the investigator will be listed.

For laboratory variables (analyses of haematology, clinical chemistry, and thrombogenicity), the mean, standard deviation, median, and range will be presented per time point. Laboratory variables will also be presented graphically. Intra-individual changes between pre-infusion and the respective post-infusion time points will be analysed using shift tables and graphical presentations. Fibrinogen inhibitor testing data will be summarized in frequency tables.

For vital signs, the mean, standard deviation, median, and range will be presented per time point (original values and intra-individual changes between pre-infusion and the respective post-infusion time points). Physical examination data will be presented in frequency tables.

All adverse events for each subject will be listed in Appendix 16 of the CSR, featuring the following data:

- Subject identifier and characteristics (age, sex, weight)
- The adverse event (preferred term, reported term)
- Onset, date of resolution and duration of the adverse event
- Severity (mild, moderate, severe)
- Seriousness (serious/non-serious)
- Action taken - General (none, drug therapy, tests performed) and on study drug (dose not changed, product withdrawn, dose reduced, dose increased)

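### Thrombogenicity markers are drawn 3 h after the first bleeding infusion, 1 h after additional ones and not around the last, so post-infusion changes cannot be compared like for like and the last repeat dose is unmeasured

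*Protocol*

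**What the plan says.** Protocol 3.1.2.3 lists as a safety endpoint "Thrombogenicity testing before and after each IMP infusion for the treatment of bleeding, except on the Day of Last Infusion". The synopsis and SAP 4.3.7 carry the same wording, and none of the three gives a reason for the exception. Protocol Table 5 names the markers as D-dimer and prothrombin fragment 1+2, measured centrally in citrated plasma.

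The schedule for a bleeding episode is:

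- **First infusion (Protocol 6.1.3.1):** markers before the infusion and at 3 h. The 1-h list has fibrinogen and clot firmness only.
- **Additional infusions (6.1.3.2):** markers before the infusion and at 1 h. There is no 3-h draw.
- **Last infusion (6.1.3.3):** this section applies "If a patient requires multiple infusions for a bleeding event as defined by the investigator based on his/her judgement of the subject's condition", or at the end of the observation period. The only blood draw listed before the infusion, at 1 h and at the 24-h or end-of-observation visit is fibrinogen. The post-infusion part begins "On the Day of Last Infusion, post-infusion assessments will be as follows".

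The synopsis and the thrombogenicity row of the on-demand flow chart agree with this. On analysis, SAP section 12 says of the laboratory variables, thrombogenicity included: "Intra-individual changes between pre-infusion and the respective post-infusion time points will be analysed using shift tables and graphical presentations".

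**The concern.** Protocol 1.5 names thromboembolic events as a product risk, and these markers are the planned laboratory evidence on it. Three features weaken that evidence.

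1. The first dose is read at 3 h and later doses at 1 h. A difference in the post-infusion rise between first and repeat doses cannot be separated from the difference in sampling time, and no analysis can recover it.
2. The last infusion of a multi-infusion bleed has no marker at all. If there are only two infusions, no repeat dose is measured.
3. The exception depends on knowing that an infusion is the last. Under 6.1.3.2 the next daily fibrinogen level decides whether another follows, so whether a sample is drawn rests on a forecast of the child's course.

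The minimum number of children with an assessed bleed is 6 (Protocol 9.1). The PK and surgical schedules contain no thrombogenicity draws that could fill the gap.

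**Working it through.** The plan gives no figure of its own to reproduce: there is no sample size calculation, and the number of infusions per bleed is not stated.

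**Step 1. Scheduled marker draws**

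| Infusion | Before | 1 h after | 3 h after |
|---|---|---|---|
| First | yes | no | yes |
| Additional, not last | yes | yes | no |
| Last of several | no | no | no |

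The first and the additional infusions have no post-infusion time in common.

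**Step 2. Coverage of repeat doses.** A bleed with k infusions has k-1 repeat doses. With the exception applied as written, all of them except the last are sampled, so coverage is (k-2)/(k-1): 0/1 for k = 2, 1/2 for k = 3, 2/3 for k = 4, 5/6 for k = 7 and 6/7 for k = 8.

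**Step 3. Plausible values of k.** Inputs from the documents:

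- target and lower limit of 100 and 80 mg/dL for minor bleeds, and 150 and 130 mg/dL for major bleeds (Protocol 5.4.3);
- observation of at least 3 days (minor) or 7 days (major), with daily levels (6.1.3.2);
- a half-life of 3-5 days, which Protocol 1.1 gives for normal physiological conditions.

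Assumptions: each infusion reaches its target, decline is mono-exponential, and re-dosing follows the level rule within the minimum period. The level after 24 h is target × 2^(-1/T), with T the half-life in days. It falls below the limit when T < ln 2 / ln(target/limit):

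- minor: 0.6931 / ln(100/80) = 0.6931 / 0.2231 = 3.11 days
- major: 0.6931 / ln(150/130) = 0.6931 / 0.1431 = 4.84 days

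| Bleed | T (days) | Level at 24 h (mg/dL) | Infusion days | k | Repeat doses sampled |
|---|---|---|---|---|---|
| Minor | 3 | 79.4 | 1, 2, 3 | 3 | 1/2 (50%) |
| Minor | 4 | 84.1 | 1, 3 | 2 | 0/1 (0%) |
| Minor | 5 | 87.1 | 1, 3 | 2 | 0/1 (0%) |
| Major | 3 | 119.1 | 1 to 7 | 7 | 5/6 (83%) |
| Major | 4 | 126.1 | 1 to 7 | 7 | 5/6 (83%) |
| Major | 5 | 130.6 | 1, 3, 5, 7 | 4 | 2/3 (67%) |

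If the period runs through Day 4 or Day 8 instead, the 3-day minor case becomes k = 4 (2/3, 67%) and daily-dosed major bleeds become k = 8 (6/7, 86%). The other rows do not change.

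**Step 4. Sensitivity to the peak reached.** If a minor bleed peaks at 90 instead of 100 mg/dL, the 24-h level at T = 5 days is 90 × 0.8706 = 78.4, which is below 80. The rule then gives infusions on Days 1, 2 and 3, and coverage is 1/2 instead of 0/1. The two-infusion result is thus plausible but depends on the target being reached.

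**The case against.** The strongest defence is that the exception is explicit and consistent across the endpoint definition, the text and the flow chart. It is a design choice, not a contradiction, in a descriptive study where no error rate is affected. That is right. The point is a weakness of design for which no reason is given.

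Three stronger readings are tempting, and the documents do not support them.

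- A reader might infer that repeat-dose thrombogenicity is largely unmeasured. Every intermediate infusion has a pre-infusion and a 1-h draw, so at least two thirds of repeat doses are sampled in the modelled major bleeds.
- A reader might infer that the trial cannot show any rise in the markers with repeated dosing. Pre-infusion values exist before the first and each intermediate infusion, so build-up can be described. With four or more infusions, the 1-h values after intermediate doses also share one lag.
- A reader might infer that samples are missing where exposure is greatest. Dosing is top-up to a fixed target, so the modelled peak after the last infusion equals the peak after the first. With the response of 1.77 in SAP section 3 and a zero baseline, the dose formula gives a first infusion of 100/1.77 = 56.5 or 150/1.77 = 84.7 mg/kg. A Day 2 top-up at T = 3 days is (100 - 79.4)/1.77 = 11.6 or (150 - 119.1)/1.77 = 17.5 mg/kg. Only the cumulative dose is highest at the last infusion.

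Two further objections have force. If an infusion is recognised as the last only afterwards, the additional-infusion lists would have applied and its samples may exist. That softens the gap, but it also confirms that the exception cannot be applied uniformly. Table 5 also provides for remaining plasma to be stored and allows additional coagulation testing, so some samples may be recoverable. Clinical monitoring continues in any case: the thromboembolic questionnaire is completed around the last infusion and at Day 30, and adverse events are recorded.

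**Conclusion.** The concern holds as a limited and avoidable design weakness. Two parts follow from the schedule alone: post-infusion changes cannot be compared like for like between first and repeat doses, and with the exception applied as written the last repeat dose has no marker. In a two-infusion bleed that leaves no repeat-dose marker.

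The size depends on the number of infusions, which the documents do not give. Under the assumptions above, minor bleeds have two infusions when the half-life exceeds about 3.1 days. Repeat-dose coverage is then 0-50% in minor bleeds through Day 3 (67% at a 3-day half-life if Day 4 counts) and about 67-86% in major bleeds. The half-life is quoted for normal physiology and may not fit bleeding children with fibrinogen deficiency, and treatment duration is also left to the investigator's judgement. The percentages are therefore illustrative. Correction is worthwhile because it is cheap.

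**What to change.** **Protocol**

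- Delete the last-day exception from the thrombogenicity endpoint in the synopsis and in 3.1.2.3.
- Add thrombogenicity to the pre-infusion and 1-h lists for the last infusion (synopsis and 6.1.3.3) and to the Day 1 1-h list (synopsis and 6.1.3.1). Keep the Day 1 3-h sample.
- Align the on-demand flow chart. Reconcile its footnote [f], which sends single-infusion bleeds to the Day of Last Infusion assessments, with the 3-h marker draw in 6.1.3.1.
- If there is a reason to leave out the last infusion, state it, and still give first and additional infusions one common post-infusion time.

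**SAP**

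- Delete the same exception in 4.3.7.
- Add a thrombogenicity sub-table to table 14.3.11. It lists only haematology and clinical chemistry, although section 12 promises thrombogenicity summaries.
- Show the 1-h change for first versus repeat infusions, as a listing if numbers are small. Note that repeat dosing will still be confounded with time since the bleed began.

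**Cost.** Citrated plasma for central fibrinogen is already drawn at all three added times, so no visit or venepuncture is added. The extra work is two assays on up to three samples per bleed, at most 3 × 2 = 6 results. Each draw needs slightly more plasma, and in small children that volume must be confirmed against the laboratory manual.
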